6.2.1 Concomitant therapy

The investigator must instruct the participant to notify the study site about any new medications he/she takes after the participant is enrolled into the study.

All medications, vaccines, procedures, and significant non-drug therapies (including physical therapy and blood transfusions) administered after the participant was enrolled into the study must be recorded on the appropriate case report forms (CRF).

Each concomitant drug must be individually assessed against all exclusion criteria/prohibited medication. If in doubt, the investigator should contact the Novartis medical monitor before randomizing a participant or allowing a new medication to be started. If the participant is already enrolled, contact Novartis to determine if the participant should continue participation in the study. There are no restrictions related to COVID-19 vaccines, and these are allowed throughout study participation as permitted by local regulations.

Drugs to control medically significant lipid abnormalities (which have been confirmed upon repeat testing) can be prescribed according to local standard of care. Participants on medications specified in Table 6-2 can be included if these medications are medically necessary, and the investigator feels the dose will remain stable for the duration of the double-blind treatment period. In addition, doses of oral anti-diabetic medication, insulin, GLP-1 agonists, thyroid hormone, and estrogen or estrogen containing birth control, must be stable for at least 3 months prior to the Baseline visit. Sliding scale insulin therapy is allowed if this approach has been implemented for at least 3 months prior to the Baseline visit. Insulin dose adjustment is permitted during the study if required. Doses of vitamin $E \leq 800$ IU/day must be stable for at least 6 months prior to the Baseline visit. A stable dose is defined as a dose within 25% of the Baseline dose. New use or dose adjustments > 25% of the Baseline dose of these medications is not allowed after entering the study.

Table 6-2	Medications permitted only if dose is stable (within 25 percent of
	Baseline dose) and expected to remain stable through the double-
	blind treatment period

Medication	Stable dose start
Oral anti-diabetic medications	At least 3 months prior to the Baseline visit
Insulin	At least 3 months prior to the Baseline visit

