GLP-1 agonists such as liraglutide, exenatide, lixisenatide, albiglutide or dulaglutide	At least 3 months prior to the Baseline visit
Beta-blockers and thiazide diuretics	At or before Screening Visit 1
Vitamin E < 800 IU/day	At least 6 months prior to the Baseline visit
Thyroid hormone	At least 3 months prior to the Baseline visit
Phenothiazines	At or before Screening Visit 1
Estrogen or estrogen containing birth control	At least 3 months prior to the Baseline visit

6.2.2 **Prohibited medication**

Use of the treatments displayed in the below Table 6-3 is NOT allowed after the start of investigational drug, and should be discontinued as soon as screening is considered so that participants medications and conditions are stable and the screening assessments reflect the participant's Baseline condition.

Alcohol consumption is to be strongly discouraged, and if consumed should not exceed 20 g/day (14 units/week) in females and 30 g/day (21 units/week) in males. A "unit" of alcohol is equivalent to 12-ounce, 355 ml beer, 4-ounce, 120 ml glass of wine, or 1 ounce, 30 ml shot of hard liquor.

Use of methotrexate is prohibited as liver fibrosis has been reported with its chronic use.

A study in healthy volunteers was conducted to investigate the effect of UDP glucuronosyltransferase (UGT) inhibition on the pharmacokinetics (PK) of tropifexor by coadministration with the UGT1A1 inhibitor, atazanavir (ATZ) (CLJN452A2110). The inhibition of UGT1A1 by ATZ did not lead to increased exposure of tropifexor, suggesting that inhibition of the UGT1A1 pathway has no clinically relevant impact on tropifexor PK. Therefore, no Drug-Drug Interactions are expected between tropifexor and UGT1A1 inhibitors based on UGT1A1 activity / genotype, and therefore use of these compounds is not prohibited in this study. Non-selective UGT inhibitors are prohibited.

Medication	Timing
SGLT2 Inhibitors or combined SGLT1/2 inhibitors	Stop at least 3 months prior to Baseline
Such as: canagliflozin, dapagliflozin, empagliflozin	
Pharmacologically active weight-loss medications	Stop at least 3 months prior to Baseline
Such as: lorcaserin, phentermine/topiramate, bupropion-naltrexone HCL, orlistat)	
Treatment with drugs that have a high incidence of diarrhea	Stop at or before Screening Visit 1
Such as: Orlistat, Acarbose.	
Treatment with drugs that alter intestinal motility	Stop at or before Screening Visit 1

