# 2.5 Analysis of the primary objective

The primary objective of the study is to demonstrate the efficacy of tropifexor + licogliflozin as assessed by histologic improvement after 48 weeks of combination treatment compared to each monotherapy treatment in patients with NASH and stage 2 or 3 fibrosis.

The following estimands framework is adopted to evaluate the objective.

- 1. Population: Full Analysis Set (FAS), for the adult population with NASH and stage 2 or 3 liver fibrosis as further defined with study inclusion and exclusion criteria.
- Variables of interest: histological response defined as resolution of NASH (absence of ballooning with no or minimal inflammation by histology) and no worsening of fibrosis OR improvement in fibrosis by at least one stage without worsening of NASH (worsening of hepatocellular ballooning or lobular inflammation) at week 48 compared with baseline. The criteria for changes in histologic endpoints are further detailed in Section 5.3.11.
- 3. Summary measure: odds ratio for the proportion of patients achieving histological response at week 48 between the combination and each monotherapy treatment.
- 4. Intercurrent events include
  - Early discontinuation of study treatment or withdrawal from study before week 48 visit.
  - Non-histologic clinical event suggesting treatment failures (e.g progression to cirrhosis, liver transplant and death due to disease).
  - Study treatment incompliance defined as relative dose intensity >1.25 or <0.75.
  - More than four weeks of accumulative exposure to any prohibited medications (Protocol Section 6.2.2), alcohol usage more than what is permitted in the protocol, initiation of other T2DM or lipid lowering medication (e.g. GLP-1 modulator), initiation of other treatment being evaluated or approved for NASH, or new concomitant interventions for weight control (e.g bariatric surgery) before the assessment for primary endpoint. The identification of relevant medications will be based on ATC3 and/or ATC5 codes, which will be included in analysis data set specifications. The list of concomitant interventions with significant effect for general weight loss will be determined based on blinded review of the study data.

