All practical measures will be exercised in the study to collect as much data as possible at week 48 despite intercurrent events (e.g. early discontinuation of study treatment). In the case of early withdrawal from the study on or after week 24, patient's histological response will be assessed if possible at the early termination visit.

A combination of the while-on-treatment and hypothetical strategies as defined in ICH E9 (R1) on handling intercurrent events will be adopted for the primary analysis.

If a patient discontinued study treatment early or withdrew early from the study without other inter-current event, but has histological response status collected after at least 24 weeks of study treatment, the primary endpoint will be imputed with their last histological response status

Novartis	For business use only	Page 20
SAP		CLJN452D12201C

assessed after at least 24 weeks of treatment. Patients with missing primary endpoint or primary endpoint after inter-current event(s) will have their primary endpoint data imputed with a multiple imputation (MI) method as outlined in Section 2.5.3 to estimate the treatment effect that would have been observed if all patients had continued on treatment for 48 weeks without intercurrent event.

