#### 5.1.2 AE start and stop dates

#### **AE Start Date Imputation:**

AE start date with missing year or with missing month but non-missing day will be resolved through data queries.

Defining AE reference date as

- If AE end date (after imputation if needed) <= first dose date, AE reference date = min (informed consent date, earliest visit date of SVs)
- Else AE reference date = first dose date

and following date components

	Day	Month	Year
Partial AE Start Date		MON	YYYY
AE reference Date	REFD	REFM	REFY

incomplete AE start date will be inputted according to logic matrix

(Imputation)	MON MISSING	MON < TRTM	MON = TRTM	MON > TRTM
YYYY MISSING	NC	NC	NC	NC
YYYY < TRTY	(D)	(C)	(C)	(C)
YYYY = TRTY	(B)	(C)	(B)	(A)
YYYY > TRTY	(E)	(A)	(A)	(A)

where

NC	No convention - require data query
(A)	01-MON-YYYY
(B)	AE reference date
(C)	Last day of month MON-YYYY
(D)	Last day of year YYYY
(E)	01-JAN-YYYY

Novartis	
SAP	

The algorithms will be reflected in the Variable Source Derivation column as #IMPUTAEV (*event*) where *event* is the incomplete start date of the adverse event.

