#### **AE End Date Imputation:**

If all AE end date components are missing after data queries, the AE is considered ongoing for analysis purpose.

If AE end month is missing, the AE end date is imputed as the last day of AE end year or patient's study completion/discontinuation visit date, whichever is earlier.

If AE day is missing, then AE end date is imputed as the last day of the month or patient's study completion/discontinuation visit date, whichever is earlier.

If imputed AE end date is less than the AE start date, use the AE start date as the imputed AE end date.

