# 5.1.3 Start and stop dates of prior/concomitant medications or non-drug therapies / procedures

The imputation for incomplete start or stop date of medications or non-drug therapies / procedures patients received in addition to study treatment during the study will follow the same algorithms for imputations of incomplete AE start/stop date.

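### The SAP dates incomplete medication records with the adverse-event rule, so some pre-baseline drugs can look like on-treatment starts or on-treatment use

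*SAP*

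**What the plan says.** SAP 5.1.3, whose heading covers both prior and concomitant medications, gives no rule of its own. Incomplete dates "will follow the same algorithms for imputations of incomplete AE start/stop date".

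The borrowed rule is in SAP 5.1.2.

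- **Stop dates.** "If AE end month is missing, the AE end date is imputed as the last day of AE end year", or the study completion/discontinuation visit if that is earlier. With only the day missing, the last day of the month is used under the same cap. With everything missing after queries, the record is treated as ongoing.
- **Start dates.** These depend on a reference date. The rule begins "If AE end date (after imputation if needed) <= first dose date, AE reference date = min" of the consent date and the earliest visit date; otherwise, "Else AE reference date = first dose date". A start in the reference year with the month missing, or in the reference month with the day missing, is set to the reference date.

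SAP 2.5 lists medication-related intercurrent events. They include "More than four weeks of accumulative exposure to any prohibited medications" and the initiation of other T2DM or lipid-lowering medication. On handling, it states: "Patients with missing primary endpoint or primary endpoint after inter-current event(s) will have their primary endpoint data imputed". SAP 2.5.3 and protocol 12.4.4 say the same.

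Protocol 2.1 and 12.4.3 item 3 differ. A medication change is ignored in the primary analysis (treatment policy), and imputation as if it had not occurred is kept for a supplementary analysis.

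**The concern.** For an adverse event, moving a doubtful date into the treatment period is the cautious choice. For a medication it can create an exposure or an initiation that did not happen.

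It can also contradict data the trial already holds. Protocol 8.2.6 captures medications at screening and updates them at Baseline. Protocol 6.2.1 says that doses of anti-diabetic drugs, among others, "must be stable for at least 3 months prior to the Baseline visit". Table 6-3 gives SGLT2 inhibitors the timing "Stop at least 3 months prior to Baseline". A drug on the screening record cannot have started on the day of first dose, yet the rule can say that it did.

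The two artefacts, false initiation and false prolonged use, match two of the SAP 2.5 intercurrent events. If the imputed dates feed that flag, an observed Week 48 biopsy result could be set aside because a participant could not recall the month of an old prescription. Genuine lipid-drug starts are also expected, since protocol 10.2.3.2 encourages their early introduction, and false starts would be indistinguishable from them.

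**Working it through.** **Inputs.** The start matrix and stop rule come from SAP 5.1.2, applied through 5.1.3. The four-week threshold (28 days) comes from SAP 2.5. The matrix uses TRTM and TRTY, which are not defined there; they are read as the month and year of the reference date.

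**Tracing records.** The example takes first dose on 15 June 2020 and follow-up of 365 days.

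| Record | Imputed result | Days from first dose |
|---|---|---|
| Start 2020, stop 2020, months unknown | 15 Jun to 31 Dec 2020 | 200 |
| Start 2018, stop 2020, months unknown | stop 31 Dec 2020 | 200 |
| Start 2020, month unknown, ongoing | start 15 Jun 2020 | apparent initiation |
| Start 2019, stop fully missing after queries | ongoing | 365 |
| Start and stop Jun 2020, days missing | 15 to 30 Jun 2020 | 16 |
| Start 2020 month unknown, stop 10 Mar 2020 complete | pre-treatment | 0 |
| Start Feb, stop Mar 2020, days missing | pre-treatment | 0 |
| Start and stop 2019, months unknown | pre-treatment | 0 |

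The 200 days are 16 + 31 + 31 + 30 + 31 + 30 + 31 (June to December). They arise even if the drug was in fact stopped in January.

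**How often a same-year, month-missing stop crosses four weeks.** False days = 31 December − first dose + 1. This exceeds 28 for any first dose up to 3 December, day 337 of a 365-day year: 337/365 = 92%. If the first 90 days of the year are left out, because a 3-month washout after a same-year stop could not fit, the share is (275 − 28)/275 = 247/275 = 90%. Leaving out 182 days for a 6-month washout gives (183 − 28)/183 = 155/183 = 85%.

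**Same-month stop with only the day missing.** More than 28 days needs a first dose on days 1 to 3 of a 31-day month or days 1 to 2 of a 30-day month: (7 × 3 + 4 × 2)/365 = 29/365 = 8%, with a maximum of 31 days.

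**What replacement would cost in power.** First, the SAP's own figure in Table 3-2: 70 per arm, 25% against 45%, one-sided alpha 0.05, pooled z-test.

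- Null SE = √(2 × 0.35 × 0.65/70) = 0.0806.
- Alternative SE = √((0.25 × 0.75 + 0.45 × 0.55)/70) = 0.0788.
- Power = Φ((0.20 − 1.645 × 0.0806)/0.0788) = 80.4%, against the stated 80%.

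Now suppose a share f of results in every arm is replaced by draws from an imputation model without treatment, as in SAP 5.4.2. The common rate is (25 + 45 + 25)/3 = 31.7%, so each arm's rate becomes (1 − f) × own rate + f × 31.7%. For f = 2%, 5% and 10%, power is 78.9%, 76.7% and 72.7%. These values of f are assumptions, since the documents give no frequency of partial medication dates.

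**The case against.** The strongest case against has five parts.

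1. **The current protocol keeps the biopsy.** Protocol 2.1 and 12.4.3 item 3 ignore medication changes in the primary analysis, and the estimand's treatment attribute allows anti-diabetic and lipid-lowering changes. The SAP dates from December 2019 and describes the three-arm, 210-patient design. This stands in large part. Protocol 12.4.4, however, still carries the sentence imputing any endpoint after an intercurrent event, so the conflict is live.
2. **The link to the flag is inferred.** No text says that imputed dates define intercurrent events, and SAP 2.5 leaves drug identification to data set specifications. This stands as a limit. Still, 5.1.3 is the only medication-date rule and SAP 2.1 shows listings without imputation, so the imputed dates must serve some analysis.
3. **The body of 5.1.3 refers to treatments received during the study.** That may leave out drugs stopped before baseline, although the heading includes prior medications. Ongoing background drugs are covered on either reading.
4. **Queries catch some gaps.** SAP 5.1.2 sends a start with the year missing, or the month missing but the day known, to query. A stop is treated as ongoing only after queries. Protocol 11.2 queries missing values, and 11.3 requires full verification of eligibility and primary-variable data. This lowers the frequency but does not correct the rule for what remains.
5. **The supportive intent-to-treat and CMH analyses in SAP 2.5.4 use the observed result.** They would help show an effect but do not repair the primary analysis.

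A reader might infer that partial medication dates in general are misplaced. The trace shows otherwise: complete pre-baseline stops, prior-year records and day-only gaps in earlier months stay before treatment. Nor do all affected drugs leave the prior-therapy count. A drug with an earlier-year start remains prior under SAP 2.4.2; only one whose start is moved to first dose drops out.

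**Conclusion.** The point holds in a limited form. As written, SAP 5.1.3 gives wrong dates for a narrow set of records: partial starts in the first-dose year or month for drugs not known to have stopped by first dose, month-missing stops in the first-dose year, and fully missing stops that queries do not resolve. Given a same-year, month-missing stop before baseline, false use exceeds four weeks for 92% of first-dose dates (about 90% where a 3-month washout fits).

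The consequence depends on two things that the documents leave open: whether imputed dates set the intercurrent-event flag, and which handling rule governs. Under SAP 2.5/2.5.3 and protocol 12.4.4, an observed Week 48 result would be replaced. Under protocol 2.1 and 12.4.3 item 3, the efficacy effect is confined to the supplementary hypothetical analysis. The prior/concomitant summaries could be affected either way.

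A reader might conclude that the primary analysis will discard valid biopsies, or that some percentage of them will be lost. The documents support neither. A loss would need a listed drug, one of these date patterns, an observed biopsy and the SAP's handling rule all together, and no frequency is given for any such combination. The power figures only illustrate assumed shares.

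**What to change.** When the SAP is updated for the amended protocol:

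- Give medications their own date rule in 5.1.3. If a drug was recorded at Screening or Baseline as already taken, cap a partial start at the day before first dose. If it was recorded at Baseline as stopped, cap a partial stop at the day before first dose. Keep the adverse-event rule only for drugs first recorded after first dose.
- Query partial dates for every drug on the intercurrent-event list before database lock.
- State which dates, collected or imputed, set the intercurrent-event flag.
- Reconcile protocol 12.4.4 and SAP 2.5/2.5.3 with protocol 12.4.3 item 3.

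The cost is SAP wording (with the matching protocol clarification), a small change to the derivation program and a few data queries. No new assessments are needed.

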#### 5.1.4 Other imputations

Imputation of missing primary or secondary endpoints are included in corresponding sections 2.5, 2.6 and 2.7 for the corresponding analyses. There will be no imputation for other analysis in this SAP.

# 5.2 AEs coding/grading

AEs are coded using the latest version of MedDRA dictionary practically implementable before study database lock.

#### 5.3 Derivations

#### 5.3.1 Laboratory parameters

Laboratory criteria of potential hepatotoxicity for liver safety monitoring in protocol section 10.2.1 (not including additional non-lab criteria):

- ALT or AST  $> 5 \times ULN$ 

- $ALP > 2 \times ULN$
- TBL >  $2 \times ULN$
- ALT or AST  $> 3 \times$  ULN and INR > 1.5
- ALT or AST > 3  $\times$  ULN and TBL > 2  $\times$  ULN AND ALP to  $\leq$  2  $\times$  ULN (Potential Hy's Law cases)
- ALT or AST  $> 3 \times ULN$

Laboratory criteria of potential nephrotoxicity for renal safety monitoring in protocol section 10.2.2:

- Two or more consecutive serum creatinine increase  $\geq 25\%$  compared with baseline
- serum creatinine increase  $\geq 50\%$  compared with baseline
- $eGFR < 60 \text{ mL/(min*1.73m^2)}$
- Two or more consecutive albumin- or protein-creatinine ratio increase  $\geq$  2-fold
- Two or more consecutive albumin-creatinine ratio (ACR)  $\geq$  30 mg/g;
- Two or more consecutive protein-creatinine ratio (PCR)  $\geq$  150 mg/g
- Dipstick glycosuria  $\geq 1+$  for patients with negative reading at baseline
- Dipstick hematuria ≥ 1+ not due to trauma for patients with negative reading at baseline

Criteria for other notable laboratory abnormality:

Parameter	Threshold value	Unit	
Albumin	<32	g/L	
Hemoglobin	<70	g/L	
Hemoglobin	>200	g/L	
White blood cell count	<2.0	10  /L	
White blood cell count	>35.0	10  /L	
Platelets	<50	10  /L	
Platelets	>1000	10  /L	
INR	>4.0		
PT	>40.0	sec	
APTT	>80.0	sec	
Sodium	<120	mmol/L	
Sodium	>160	mmol/L	
Potassium	<3.0	mmol/L	
Potassium	>6.0	mmol/L	
Glucose	<2.2	mmol/L	
Glucose	>27.8	mmol/L	
Calcium	<1.50	mmol/L	
Calcium	>3.00	mmol/L	
Phosphate	<0.29	mmol/L	
Creatinine	>177	µmol/L	

**Table 5-1**Notable criteria for other laboratory parameters

Novartis SAP	For business use only	CLJN452E	Page 39 012201C
Calculated eGFR	<60	mL/min	

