10.2 Additional Safety Monitoring

10.2.1 Liver safety monitoring

To ensure participant safety and enhance reliability in determining the hepatotoxic potential of an investigational drugs, a standardized process for identification, monitoring and evaluation of liver events has to be followed.

The following two categories of abnormalities / adverse events have to be considered during the course of the study (irrespective of whether classified/reported as AE/SAE):

- Liver laboratory triggers, which will require repeated assessments of the abnormal laboratory parameter
- Liver events, which will require close observation, follow-up monitoring and contributing factors are recorded on the appropriate CRFs

Please refer to Section 16.2 for complete definitions of liver laboratory triggers and liver events.

Elevations in ALT and AST during study conduct must be reviewed in the context of participant's baseline value, prior to study medication initiation. Participants with baseline values of ALT or AST > $5 \times$ ULN are excluded.

Participants who develop elevations in liver-related laboratory parameters and/or clinical symptoms suggestive of liver disease should be managed according to Table 16-2. If ALP, ALT, AST, or bilirubin elevations reach the specified thresholds outlined in Table 16-2, the participant must return to the study site for re-evaluation within 48 to 72 hours after the laboratory results becoming available, at which time central confirmatory laboratory testing will be performed. This includes ALP, ALT, AST, total and direct bilirubin and INR.

If prompt evaluation is not

possible within 48 to 72 hours following receipt of abnormal laboratory results, study drug should be interrupted immediately (date of last study drug dose must be recorded in the eCRF) and the participant must return to the study site as soon as possible for re-evaluation. The sponsor should be notified of laboratory abnormalities and any clinical symptoms within 48 hours of available laboratory results and/or assessment of clinical symptoms.

If the elevation is confirmed, close observation of the participant will be initiated, including consideration of treatment interruption or discontinuation (as described in Table 16-2) if deemed appropriate and close monitoring, causality and clinical evaluation should be performed as below;

- Repeating the liver tests to confirm elevation as described in Table 16-2

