12.5.2.2 Clinical laboratory evaluation

Summary statistics for standard laboratory test results will be provided by treatment and visit/time. Shift tables using the low/normal/high/ (low and high) classification will be used to compare baseline to the worst on-treatment value.

Number (percent) of participants with post-treatment changes in lab parameters related to hepatotoxicity (ALP, ALT, AST, or bilirubin elevations as outlined in Section 10.2.1 and Table 16-2) will also be summarized.

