12.5.2.4 ECG

PR, QRS, QT, QTcF, and RR intervals will be obtained from 12-lead ECGs for each participant during the study. ECG data will be read and interpreted centrally.

Number of participants changing in normal or abnormal ECG will be summarized by treatment and scheduled visit.

The Fridericia QT correction formula (QTcF) will be used for clinical decisions and for analyses. Notable QTcF values and changes from baseline will be summarized by treatment and scheduled visit, where a notable value is defined as a QTcF \geq 450 msec (male) or \geq 460 msec (female) and the categories used for the change (increase) in QTcF are: \leq 30 ms, > 30 to \leq 60 ms and > 60 ms.

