#### 2.8.3 Laboratory data

Summary statistics of values and changes from baseline will be provided by visit (AV2) and by study treatment for laboratory tests listed in Table 2-6. Change from baseline will be summarized for patients with both baseline and post baseline values.

laboratory test group	Parameters	
Hematology	Hemoglobin (Hb), Hematocrit (Hct), Red blood cells (RBC), Mean corpuscular volume (MCV), Platelets, White blood cells (WBC), absolute WBC differential counts ((Neutrophils, Lymphocytes, Monocytes, Eosinophils, Basophils separately)	
General Clinical Chemistry	Sodium, potassium, chloride, bicarbonate, calcium, magnesium, phosphorus, uric acid, haptoglobin	
Liver	ALT, AST, ALP, GGT, creatine kinase (CK), lactate dehydrogenase (LDH), total bilirubin, albumin, total protein	
Renal	BUN, creatinine, estimated glomerular filtration rate (eGFR)	
Urinalysis	Albumin-creatinine ratio (ACR), Protein-creatinine ratio (PCR)	
Coagulation	INR, APTT, Prothrombin Time (PT) and Thrombin Time (TT)	
Lipids and vascular risk	Total cholesterol, HDL-C, LDL-C, VLDL-C, triglycerides, free glycerol and free fatty acids, ApoAI, high sensitivity C-reactive protein (hsCRP)	

 Table 2-6
 Laboratory safety endpoints

Shift tables for normal / abnormal (low and high based on the low/normal/high classifications from central lab) from baseline to the most extreme post-baseline value will be provided.

Number (%) of patients with post-treatment changes in laboratory criteria related to hepatotoxicity or nephrotoxicity criteria (Section 5.3.1) will also be summarized by criteria and by study treatment. In addition, patients meeting a criterion for hepatotoxicity, nephrotoxicity or other notable abnormalities defined in Section 5.3.1 will be listed, including the criteria met as well as the laboratory test name, date (study day) of lab sampling, results and units for that test and related lab tests throughout the study.

Novartis	For business use only	Page 28
SAP		CLJN452D12201C

For summaries of shift, hepatotoxicity/nephrotoxicity events or other notable laboratory abnormalities outlined above, all post-treatment data will be used regardless of last dose date.

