# 2.8.4 Other safety data

#### 2.8.4.1 ECG and cardiac imaging data

The PR, QRS, QT, QTcF, and RR intervals will be summarized by visit and by study treatment.

Number (%) of patients shifting from baseline in the overall normal or abnormal ECG abnormality will be presented by visit and by study treatment.

The Fridericia QT correction formula (QTcF) will be used for clinical decisions and for analyses. Notable QTcF values and changes from baseline will be summarized as categorical variable by visit and by study treatment, where a notable value is defined as a QTcF interval of greater than 450 ms and the categories used for the change (increase) in QTcF are:  $\leq$  30 ms, > 30 to  $\leq$  60 ms and > 60 ms.

[figure not shown]

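### The December 2019 SAP was not updated after Amendments 01 and 02, so specific liver, renal and QTcF safety criteria no longer match the protocol

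*SAP*

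**What the plan says.** **Liver.** SAP 5.3.1 lists laboratory criteria of potential hepatotoxicity "for liver safety monitoring in protocol section 10.2.1 (not including additional non-lab criteria"). There are six rows: ALT or AST above 5 x ULN; ALP above 2 x ULN; total bilirubin (TBL) above 2 x ULN; ALT or AST above 3 x ULN with INR above 1.5; a Hy's-law row; and ALT or AST above 3 x ULN alone. SAP 2.8.3 uses the list as follows: "Number (%) of patients with post-treatment changes in laboratory criteria related to hepatotoxicity or nephrotoxicity criteria (Section 5.3.1) will also be summarized".

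Protocol 12.5.2.2 plans the same table on "elevations as outlined in Section 10.2.1 and Table 16-2". Protocol 10.2.1 states: "Elevations in ALT and AST during study conduct must be reviewed in the context of" the participant's own baseline value. Table 16-2 sets its ALT, AST and ALP rows by baseline level.

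**Renal.** The SAP 5.3.1 renal list cites protocol 10.2.2, which points to Table 16-3. It includes "Two or more consecutive protein-creatinine ratio (PCR") of at least 150 mg/g, dipstick glycosuria of 1+ or more, and dipstick hematuria of 1+ or more.

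**QTcF.** SAP 2.8.4.1: "a notable value is defined as a QTcF interval of greater than 450 ms", for both sexes. Protocol 12.5.2.4: "where a notable value is defined as a QTcF" of at least 450 ms in men or at least 460 ms in women.

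**The concern.** A table of post-treatment laboratory changes should count participants whose values changed. With a fixed multiple of ULN and an entry rule that admits high enzymes, the ALT/AST row can count disease present at entry. Where the other cut-offs differ, the SAP table and the protocol's alert criteria will give different numbers for what looks like the same event. A reader of the study report would see both sets without being told why they disagree. These tables carry no hypothesis test. They are, however, how the report will describe hepatic and renal safety for an FXR agonist combined with an SGLT1/2 inhibitor.

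**Working it through.** The plan states no count to reproduce, so the check compares definitions and applies both rules to the same participant.

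**1. ALT/AST.** Let b be the baseline in multiples of ULN. Protocol 5.2 (criterion 9c) excludes only values above 5 x ULN, so b can reach 5.
- The SAP row is met when the change from baseline exceeds 3/b - 1.
- The lowest trigger in Table 16-2 is above 3 x ULN if b < 2 (change above 3/b - 1), and above 2 x baseline if b >= 2 (change above +100%).

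| b (x ULN) | SAP row met if change exceeds | Table 16-2 met if change exceeds |
|---|---|---|
| 1.5 | +100% | +100% |
| 2.0 | +50% | +100% |
| 2.5 | +20% | +100% |
| 3.0 | 0% | +100% |
| 4.0 | -25% | +100% (8 x ULN) |
| 5.0 | -40% | +100% (10 x ULN) |

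Above 3 and up to 5 x ULN, an unchanged participant is counted by the SAP and not by Table 16-2. For b >= 2 the protocol trigger is at least 2 x 2 = 4 x ULN, which always exceeds 3 x ULN. This row can therefore only over-count. The phrase about post-treatment changes does not supply a baseline condition. The dipstick rows of the same appendix do have one (negative reading at baseline); the liver rows do not.

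**2. ALP and direct bilirubin.** Table 16-2 uses above 1.5 x ULN if baseline is at or below ULN, and above 2 x baseline if it is higher. The SAP uses above 2 x ULN throughout.
- Baseline at or below ULN: values above 1.5 and up to 2 x ULN trigger in the protocol and are missed by the SAP (under-count).
- Baseline above ULN: 2 x ULN is below 2 x baseline, so the SAP over-counts. Entry allows ALP up to 300 IU/L. The ULN is not given. For an assumed ULN of 100 to 149 IU/L, 2 x ULN is 200 to 298, and an unchanged 300 is counted. At 150 IU/L it is not. Table 16-2 would need more than 600.
- The Table 16-2 row for direct bilirubin above 1.5 mg/dL has no counterpart in the SAP list.

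**3. Renal.**

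| Item | SAP 5.3.1 | Table 16-3 |
|---|---|---|
| Protein-creatinine ratio | >= 150 mg/g | >= 1 g/g |
| Dipstick hematuria | >= 1+ | >= 3+ |
| Dipstick glycosuria | >= 1+ | not listed |
| Dipstick proteinuria | not listed | >= 3+ |

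The protein-creatinine ratio of cut-offs is 1000/150 = 6.7. Protocol 1.1.4 describes glucosuria as what SGLT2 inhibition and licogliflozin produce. New glycosuria is therefore expected pharmacology in the two licogliflozin arms (140 + 80 = 220 of 380 planned participants), yet the SAP lists it under nephrotoxicity.

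**4. QTcF.** Women above 450 and below 460 ms are notable only in the SAP. Men at exactly 450 ms are notable only in the protocol. Protocol 5.2 (criterion 13b) admits women below 460 ms, so some could be notable under the SAP without change.

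**5. What agrees.** Four of the six liver rows cannot be met by a participant who stays at eligible entry values. ALT/AST above 5 x ULN is excluded at entry. TBL must be at or below ULN, which rules out the TBL row and the Hy's-law row. INR must be at or below ULN, which rules out the INR row if the laboratory's INR limit is not above 1.5 (assumed). TBL above 2 x ULN is also the Table 16-2 threshold for a normal baseline. The creatinine (25% and 50%), eGFR (below 60), two-fold ratio and albumin-creatinine (30 mg/g) thresholds match Table 16-3.

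**The case against.** The strongest reply is that this is one symptom of an outdated document. The only SAP version is dated 09-Dec-2019 and still describes 210 patients in three arms. The amendment log says Amendment 01 revised Tables 16-2 and 16-3 and clarified the female QTcF cut-off, and that Amendment 02 changed Table 16-2 again. SAP 1.1 says the SAP may be amended after a protocol amendment. This stands as the explanation. A reader might infer that the SAP departed from its source when it was written; the protocol of that date is not available, so the documents do not support that.

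It is also fair that SAP 2.8.1.1 already tabulates liver and renal events under protocol 16.2 and 16.3, and that SAP 2.8.3 adds changes from baseline, shift tables and listings. A reader might infer that the protocol-based count would be lost; it would not. What remains is that two tables would disagree.

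Randomisation should balance entry enzymes across arms. That limits bias between arms but does not make the counts right. Protocol 1.1.3 and 1.1.4 report ALT reductions with both drugs, so an absolute flag could clear more often on active treatment. The documents do not allow that effect to be sized.

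Finally, Table 16-2 is an action table with confirmation and symptom conditions. Copying it whole into 5.3.1 would largely duplicate SAP 2.8.1.1. That stands, and it argues for a row-by-row change.

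**Conclusion.** The point holds for specific rows: ALT/AST above 3 x ULN alone, ALP, the missing direct bilirubin row, protein-creatinine ratio, dipstick hematuria and glycosuria, and notable QTcF. Followed as written, the SAP would give wrong counts in these rows and a second, conflicting set beside the protocol-based events.

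A reader might infer that the whole liver list counts entry disease as hepatotoxicity. It does not: only the bare ALT/AST row certainly can, and ALP can depending on a ULN that is not given. A reader might also want a number of participants. Assuming that 5% to 15% enter above 3 x ULN gives 380 x 0.05 = 19 to 380 x 0.15 = 57, but no baseline ALT/AST distribution is given, so this range is illustrative and the true number is unknown.

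The primary and secondary efficacy analyses are unaffected. No view is taken here on which clinical threshold is right; the passages must be reconciled.

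**What to change.** In the SAP update that the amendments already require:
- Reconcile the ALT/AST, ALP, direct bilirubin, protein-creatinine and dipstick rows of SAP 5.3.1 with protocol 12.5.2.2 and Tables 16-2 and 16-3. State whether confirmation is required for a participant to count.
- Apply the averaged baseline already defined in SAP 2.1.1 to the ALT/AST and ALP rows.
- Keep ULN-based and Hy's-law counts as separately labelled rows, so that they are not read as changes from baseline.
- Reconcile the QTcF definition in SAP 2.8.4.1 with protocol 12.5.2.4.
- State how the SAP 2.8.3 laboratory counts relate to the SAP 2.8.1.1 event counts. Record any row deliberately left different in SAP Section 4, which now mentions none of these thresholds.

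The cost is SAP wording and derivations only. Rows that already agree need no change.
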